6.9 Safety Evaluation

The following safety evaluation will be performed based on SS.

6.9.1 Adverse Event

Adverse events (AEs) and SAEs will be medically coded with MedDRA version 26.1 or higher, and classified and statistically analyzed according to SOC and PT levels. In addition, solicited adverse events (inoculated sites (local) adverse events and non-inoculated sites (systemic) adverse events) will be classified and statistically analyzed per the provisions of the protocol. This trial will mainly be to make a statistical analysis of the TEAE, and list the AEs before vaccination in the form of a list.

This trial mainly conducts statistical analysis on adverse events that occur during vaccination, including those that occur within 28 days after each dose of vaccination. Unless otherwise specified, all adverse events mentioned below are those that occurred during the vaccination period.

The number of event, number of subjects, and incidence of the following AEs will be calculated by each group and the total. Fisher's exact test will be used to statistically test the differences between groups:

- All AEs.
- ✧ AEs related to the investigational vaccine.
- ✧ AEs unrelated to the investigational vaccine.
- AEs with an incidence rate $\geq 10\%$.
- ✧ AEs related to the investigational vaccine with an incidence rate $\geq 10\%$.
- AEs with an incidence rate $\geq 1\%$.
- ✧ AEs related to the investigational vaccine with an incidence rate $\geq 1\%$.
- AEs of different severity.
- ✧ AEs related to the investigational vaccine of different severities.
- ✧ AEs unrelated to the investigational vaccine of different severities.
- AEs of different doses.
- ✧ AEs related to the investigational vaccine of different doses.
- ✧ AEs unrelated to the investigational vaccine of different doses.
- AEs that occur within 30 minutes, 0-7 days, and 0-28 days.
- ✧ AEs related to the investigational vaccine that occur within 30 minutes, 0-7 days, and 0-28 days.
- AEs unrelated to the investigational vaccine that occur within 30 minutes, 0-7 days, and 0-28 days.
- AEs leading to dropout.
- ✧ AEs related to the investigational vaccine leading to dropout.

Meanwhile, the Kaplan-Meier method will be used to calculate the median duration of AEs and their 95% confidence intervals in each group, respectively (using the Brookmeyer & Crowley method of log-log transformation), and the log-rank test will be used to statistically test the differences between groups. The AEs after each dose of vaccination will be statistically analyzed respectively. The analysis of AEs for each dose will be based on the safety datasets of each dose.

Present the forest plots to compare the differences in the incidence rates of AEs between the two groups (test group 1 - control group 1), (test group 1 - control group 2), (test group 2 - control group 1), and (test group 2 - control group 1) according to the top ten preferred terms for incidence rates in the vaccine group.

When calculating the incidence of AEs, if the same AE occurs multiple times in the same subject, it is recorded as one occurrence. When calculating the number of events of AEs, if the same subject experiences the same AE multiple times, it is recorded multiple times. When analyzing the severity and correlation to the investigational vaccine of AEs, if the same AE occurs multiple times in the same subject, the most severe or the most relevant AE to the investigational vaccine should be selected for analysis.

Display the list of AEs related to the investigational vaccine, the list of AEs unrelated to the investigational vaccine, the list of AEs leading to drop out, and the list of Grade 3 or above AEs.

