6.1.2 Derived and Transformed Data

➤ Baseline

The last non-missing assessment on or before the first dose of vaccination will be defined as the baseline.

➤ Date Conversion

Month=days/30.4375, Year=days/365.25, rounding to 1 decimal place.

➤ Adverse Event

Occurrence time of AE (days) = Start date of AE - the corresponding vaccination date

AE duration(days) = End date of AE - Start date of AE + 1

➤ Treatment Emergent Adverse Event (TEAE)

TEAEs are defined as adverse events that occur after the first vaccination (including the day of the first vaccination) or worsen after vaccination. Programming is carried out according to the following rules:

- ❖ If the start date of adverse events is after (including simultaneously) the date of the first vaccination, they will be counted as TEAE.
- ❖ If the start date of adverse events is before the date of the first vaccination, they will be counted as non-TEAE.
- ❖ If the start date of adverse event or the date of the first vaccination is missing, making it impossible to determine whether the adverse event occurred after the first vaccination, then such adverse events shall all be counted as TEAE.

➤ Handling of incorrect vaccination

- ❖ In the immunogenicity evaluation, subjects will be analyzed according to the vaccine they were randomized to receive, in accordance with the Intention-To-Treat (ITT) principle.
- ❖ In the safety evaluation, subjects will be analyzed according to the vaccine they actually received, in accordance with the All Subjects as Treated (ASaT).

➤ Relationship of AEs

- ❖ Related to the study, vaccine means that the relationship between the adverse event and the study vaccine is "possibly related", "probably related", or "definitely related".

- ❖ Unrelated to the study vaccine means that the relationship between the adverse event and the study vaccine is "possibly unrelated" or "definitely unrelated".

➤ **Coding**

AEs, SAEs, and concomitant procedures will be encoded according to version 27.0 of the Medical Dictionary for Regulatory Activities (MedDRA). Concomitant medications/concomitant vaccines will be encoded according to the WHODD_2024-Mar-1 version of the World Health Organization Drug Dictionaries (WHODD).

➤ **Prior and Concomitant Medication**

The determination of prior and concomitant medication uses follows the following rules, respectively:

- ✓ Prior medication, medications with an end date that is before the first vaccination date.

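### The SAP sets no unit of analysis and no clustering adjustment for AE duration; if every event enters, the Kaplan-Meier intervals are too narrow and the log-rank p-values too small whenever durations correlate within a child.

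*SAP*

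**What the plan says.** SAP 6.9.1 states that "the Kaplan-Meier method will be used to calculate the median duration of AEs", with a Brookmeyer-Crowley 95% interval (log-log scale) for every group, and that "the log-rank test will be used to statistically test the differences between groups". It names no stratified, robust, frailty or bootstrap version for this analysis.

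The only definition of duration is in SAP 6.1.2 and is per event: "AE duration(days) = End date of AE - Start date of AE + 1".

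SAP 6.9.1 has repeat-event rules for other quantities:

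- **Incidence:** "When calculating the incidence of AEs, if the same AE occurs multiple times in the same subject, it is recorded as one occurrence".
- **Number of events:** "if the same subject experiences the same AE multiple times, it is recorded multiple times".
- **Severity and relatedness:** one event is selected, the worst or the most closely related, under a rule that opens "When analyzing the severity and correlation to the investigational vaccine of AEs, if the same AE occurs multiple times in the same subject".

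Duration has no such rule. The section also says: "The AEs after each dose of vaccination will be statistically analyzed respectively", on the safety set for each dose.

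**The concern.** Kaplan-Meier intervals and the log-rank test take their variance from the number of records and treat the records as independent. A child in this trial can supply many records. SAP 3.3 lists 6 local and 11 systemic solicited terms after each of two doses, and unsolicited events come on top. Symptoms of one illness, such as fever, cough and loss of appetite, tend to start and resolve together, so positive correlation of durations within a child is plausible. In that case the effective sample size is smaller than the record count. A group difference in how long reactions last could then be reported as significant more often than 5% of the time under no true difference. Safety is a stated secondary objective, and a reader of the report would take these p-values at face value.

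**Working it through.** **Is there a figure to reproduce?** No. The documents give no AE rate, number of events per child, within-child correlation or expected median duration. The size can only be shown as a range under assumptions.

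**Which unit does the text imply?** Duration is defined per event. Where the authors wanted one record per child and AE (incidence, severity, relatedness) they said so, and they did not say so for duration. Those rules also collapse only repeats of the same AE; a child's fever and cough would remain two records. The event-level reading is therefore the natural one, though the SAP does not state it.

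**Design-effect calculation.** Assumed inputs: m events per child with at least one event (1.5, 2, 3) and within-child correlation ρ (0.1, 0.2, 0.4).

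- Design effect: DE = 1 + (m − 1)ρ
- Understatement of the standard error: 1 − 1/√DE
- True two-sided error of a nominal 5% test: 2 × [1 − Φ(1.96/√DE)]

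| m | ρ | DE | SE understated by | True error |
|---|---|---|---|---|
| 1.5 | 0.1 | 1.05 | 2.4% | 5.6% |
| 1.5 | 0.4 | 1.20 | 8.7% | 7.4% |
| 2 | 0.2 | 1.20 | 8.7% | 7.4% |
| 2 | 0.4 | 1.40 | 15.5% | 9.8% |
| 3 | 0.2 | 1.40 | 15.5% | 9.8% |
| 3 | 0.4 | 1.80 | 25.5% | 14.4% |

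Worked example for the last row: DE = 1 + 2 × 0.4 = 1.8; √1.8 = 1.342; 1.96/1.342 = 1.461; two-sided tail 14.4%.

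**Check by simulation.** The formula is the equal-cluster one for a mean, so the two named methods were also simulated directly with no true group difference, 2,000 runs per setting. Assumptions, none from the documents: 300 against 150 children with at least one AE (the trial's 2:1 allocation), 1 + Poisson events per child, exponential durations with mean 4 days, no censoring, and correlation ρ through a Gaussian copula. Durations were rounded up to whole days for the log-rank test and left continuous for interval coverage.

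| Mean events | ρ | Event-level log-rank error | Coverage of 95% CI for median |
|---|---|---|---|
| 1.5 | 0.2 | 6.7% | 92.9% |
| 1.5 | 0.5 | 9.6% | 92.8% |
| 2 | 0.2 | 7.0% | 93.6% |
| 2 | 0.5 | 13.3% | 89.5% |
| 3 | 0.2 | 10.1% | 91.3% |
| 3 | 0.5 | 18.6% | 84.4% |

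With ρ = 0, or exactly one event per child, the event-level error was 4.5% to 5.3% and coverage 94.2% to 95.4%. Using one event per child in every setting gave a log-rank error of 4.5% to 5.8%. So the inflation comes from the clustering and disappears when it is removed.

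The two calculations agree in direction and rough size. At ρ = 0.2 the formula gives 6.2%, 7.4% and 9.8% for 1.5, 2 and 3 events, against 6.7%, 7.0% and 10.1% simulated. The coverage figures are indicative only, because the SAP's durations are whole days.

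**The case against.** The strongest reply is that the SAP does not state the unit. A reader might infer that it prescribes an event-level analysis, is wrong as specified, and will produce false safety differences. The documents do not support that. The per-event formula does not settle the matter, since even a longest-AE-per-child analysis must compute each event's duration first. SAP 2.1 places the table shells in a separate attachment, which may fix the layout and is not among these documents.

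Other text also reduces the clustering. SAP 6.9.1 classifies AEs by system organ class and preferred term. If duration is tabulated by term, fever and cough in one child fall into separate analyses and only repeats of the same term remain. The by-dose analyses remove correlation across doses, though not between several AEs after one dose.

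Finally, the events per child and the correlation are assumed, and AE duration is not an endpoint: the safety endpoints in protocol 7.2 are incidences, and trial success rests on immunogenicity.

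All of this stands and limits the point to a conditional one. It does not remove it. If all events enter, nothing in the plan handles the clustering. If they do not, the SAP fails to say which event represents a child, and that choice changes the median and the test.

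**Conclusion.** The point holds conditionally. The SAP applies methods that assume independent records to durations defined per event, with neither a one-record-per-child rule nor a clustering adjustment. On the event-level reading, and with positive within-child correlation, the intervals are too narrow and the p-values too small. Under the assumed 1.5 to 3 events per child and correlation of 0.1 to 0.4, the true error of a nominal 5% test is roughly 5.6% to 14%, with standard errors understated by about 2% to 25%. At zero correlation or with one record per child there is no inflation, and by-dose or by-term analyses would show less. The consequence is minor: a supportive safety table is affected, and no primary or secondary endpoint conclusion.

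**What to change.** State the unit of analysis for AE duration in SAP 6.9.1, and make the inference match it.

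- **Preferred:** keep the event-level Kaplan-Meier median, so the quantity estimated is unchanged. Take its 95% interval from a cluster bootstrap that resamples children within group, carrying all of a child's events. Replace the log-rank test with a Cox score or Wald test for group whose robust variance is clustered on child.
- **Alternative:** prespecify one record per child per dose and keep the planned methods. The rule must say which event is used. Taking the longest AE changes the quantity estimated and raises the median, so the table must be labelled accordingly.

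The cost is a sentence or two in the SAP, minor programming and slightly wider intervals.

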4.3 Sample Size

This trial requires the test group: ① the non-inferiority comparison with the control groups is established and the next statistical test is carried out; ② when the absolute criteria of SCR and SPR are achieved, the trial can be considered as successful and a positive conclusion can be drawn for the test group. In this trial, when evaluating between the test group 1 (0.25-mL QIV) and test group 2 (0.5mL-QIV), the strategy of sequential test is adopted. First, test group 2 is evaluated. If the positive conclusion of test group 2 is established, test group 1 is further evaluated. Therefore, class I error correction is no longer carried out. The sample size of phase III clinical trials is estimated first by non-inferiority design, namely the QIV group is non-inferior to the TIV group. The primary endpoints of this study include two indicators: SCR and GMT. Only when the SCR and GMT of four serotypes in test group are non-inferior to the control vaccine, the investigational vaccine is considered to be non-inferior to the control vaccine. The total power is 80%, the type II error is 0.2. Based on the different sample size requirements of the two indicators, the type II error is allocated, with 0.16 for SCR comparison and 0.04 for GMT comparison.

(1) Calculation of sample size with the SCR as the indicator:

According to the results of the previous Anflu phase IV clinical trial and other literature, the SCR of the types contained in the vaccine 28 days after vaccination is over 65%, which is used as the reference proportion to estimate the sample size. The test level is taken as one-sided $\alpha=0.025$, the power of non-inferiority comparison for the SCR of a serotype is taken as $1-\beta1/4=1-0.16/4=96\%$, and the non-inferiority threshold Δ is taken as -10%. When comparing the non-inferiority of BY or BV strain, NT:NC=2:1, and PASS software is used to calculate the sample size, the test group needs 914 samples and the control group needs 457 samples. When the non-inferiority test of H1N1 or H3N2 strain is carried out, two control groups are pooled. The sample size ratio of the test group and the pooled control group is 1:1, and the test group and the pooled control group need 625 participants.

(2) Calculation of sample size with the GMT as the indicator:

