Using the antibody GMT 28 days after vaccination as the outcome measure, the non-inferiority margin is $\geq 2/3$ of the 95%CI lower limit of GMT ratio between the test group and the control group, and the non-inferiority margin after logarithmic conversion is $\Delta=-0.176$. The test level is taken as one-sided $\alpha=0.025$, and the power of a certain serotype GMT for non-inferiority comparison is taken as $1-\beta2/4=1-0.04/4=99\%$, and the standard deviation after logarithmic transformation is taken as $\sigma = 0.7$ with

reference to the previous research results. When comparing the non-inferiority of BY or BV, NT:NC=2:1, and PASS software is used to calculate the sample size, the test group needs 874 samples and the control group needs 437 samples. When the non-inferiority test of H1N1 or H3N2 type is carried out, two control groups are pooled. The sample size ratio of the test group and the pooled control group is 1:1, and the test group and the pooled control group need 582 participants each.

When the SCR and GMT of the test group reach the hypothesis of non-inferiority, the absolute criteria of the SCR and seroprotection rate (SPR) of the test group are further hypothesized for test. The trial requires that the SCR and SPR of the four strains of immune antibodies reach the absolute criteria, and the total power of the trial is 80%, so the power of each test is $1 - (0.2/8) = 0.975$.

(3) Calculation of sample size with the absolute criteria of SCR:

Assuming that the SCR after vaccination is 65%, the test level is one-sided $\alpha=0.025$, the lower limit of the confidence interval of the SCR should be greater than 30%, and the power of each test is 97.5%. The sample size is calculated by PASS software, and the test group needs 28 samples.

(4) Calculation of sample size with the absolute criteria of SPR:

Assuming that the SCR after vaccination is 75%, the test level is one-sided $\alpha=0.025$, the lower limit of the confidence interval of the SPR should be greater than 60%, and the power of each test is 97.5%. The sample size is calculated by PASS software, and the test group needs 146 samples.

In consideration of the above the maximum sample size and the dropout rate of about 17%, the sample size of each test group is 1,100, and the sample size of each control group is 550, with a total sample size of 3,300.

5 Analysis Sets

(1) Immunogenicity Analysis Set

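### The log-rank test on pooled AE durations can show significantly shorter AEs for a vaccine that only adds short reactions

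*SAP*

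**What the plan says.** SAP 6.1.2 defines the variable: "AE duration(days) = End date of AE - Start date of AE + 1". A child without an AE has neither date, and the SAP gives that child no value.

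SAP 6.9.1 states that "the Kaplan-Meier method will be used to calculate the median duration of AEs and their 95% confidence intervals in each group", and adds a between-group test: "and the log-rank test will be used to statistically test the differences between groups". The analysis is repeated by dose: "The AEs after each dose of vaccination will be statistically analyzed respectively". Section 6.9 sets the population: "The following safety evaluation will be performed based on SS".

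For duration, the text does not say:
- whether the unit is the event or the child;
- whether groups are compared in pairs or all four together;
- whether related and unrelated AEs, or individual terms, are kept apart.

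The same section tests incidence for all, related and unrelated AEs, by severity, dose and time window: "Fisher's exact test will be used to statistically test the differences between groups". The safety endpoints in Protocol 7.2 are all incidences. AE duration is not among them.

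**The concern.** Being in the safety set does not give a child without an AE a duration. The log-rank test therefore compares subsets formed after vaccination, and the vaccine itself influences who enters them. As written, the pool holds local reactions such as tenderness and redness together with cough, diarrhoea and unsolicited illness up to day 28 after each dose.

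The null hypothesis is that the durations of observed AEs have the same distribution in each group. That is a different question from whether a vaccine changes how long a given kind of event lasts, or how many days a child is unwell. Extra short reactions move the distribution to the left without altering any event. The group with more reactions can then be reported as having significantly shorter AEs while its children have more AE days. This happens even with at most one event per child, so it is separate from any correlation between events in the same child.

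At stake is how one secondary safety table is read, in a trial that has the safety of both QIV doses as a stated objective (Protocol 6.2, SAP 3.1.2).

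**Working it through.** **Inputs from the documents.** Only the group sizes bear on this test: "the sample size of each test group is 1,100, and the sample size of each control group is 550". They follow from the SCR calculation, "the test group needs 914 samples and the control group needs 457 samples", and the stated dropout of about 17%: 914/0.83 = 1,101 and 457/0.83 = 551. A normal-approximation check of the SCR figure (65% in both groups, margin 10 points, one-sided 0.025, power 96%, 2:1) gives 470 control and 940 test, within 3% of the plan. The plan gives no AE rate, duration, significance level or power for the duration test.

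**Assumed inputs.** Background illness AE in 30% of each group, mean 6 days. Vaccine reactions of mean 2 days. The same duration distribution for each event type in both groups. At most one AE per child. 1,100 vs 1,100. Geometric durations capped at 28 days (the cap changes the 6-day mean only to 6 × [1 − (5/6)^28] = 5.96). Two-sided 5% test. Only the reaction rate differs: 10% in group A, higher in group B.

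**Why the mix moves.** With reaction rate r:
- mean AE days per child = 0.30 × 6 + r × 2
- mean days per AE = (0.30 × 6 + r × 2) / (0.30 + r)

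At r = 10% these are 2.0 and 2.0/0.40 = 5.0. At r = 20% they are 2.2 and 2.2/0.50 = 4.4. Burden per child rises while duration per AE falls.

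**Simulation.** Ranges are over repeated simulations of 500 to 1,500 runs where more than one was made. The Fisher columns come from 600 runs and assume that reactions are classed as related.

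| Reactions, A vs B | Days per AE | AE days per child | Log-rank significant, B shorter | Fisher, related AEs | Fisher, any AE |
|---|---|---|---|---|---|
| 10% vs 15% | 5.0 vs 4.67 | 2.0 vs 2.1 | 18-20% | 93% | 62% |
| 10% vs 20% | 5.0 vs 4.4 | 2.0 vs 2.2 | 51-53% | 100% | 99.5% |
| 10% vs 25% | 5.0 vs 4.18 | 2.0 vs 2.3 | 81-85% | 100% | 100% |

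With equal reaction rates the test rejects in about 5% of runs, as it should. When the rates differ, rejections in the opposite direction are at most 0.1%.

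**Sensitivity.**
- 1,100 vs 550, 10% vs 20%: 35-37%.
- Means of 5 and 3 days: 8%, about 23% and 38% for 15%, 20% and 25% vs 10%.
- Reactions lasting as long as background AEs (both mean 5 days, 1,100 vs 550): 2-3% one-sided, which is the nominal level.
- Other units, for a 10-point excess with background 20-30%, means of 5-7 days and reactions of mean 2 days: every AE counted 23-79%, first AE per child 39-55%, longest AE per child 14-33%. The direction does not depend on the unit.
- Across these wider scenarios, counting every AE: from about 5% for a 3-point excess to over 99% for a 20-point excess.

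**Remedies checked.** Run within related AEs alone or within unrelated AEs alone, the log-rank test rejects in about 1-5% of runs in each direction (nominal 2.5%). Stratified by event type, it stays near 5% two-sided. For mean AE days per child, with children without an AE scored 0, the 95% CI excluded zero in 7-11%, about 20% and 41-42% of runs for the three rows of the table. Long background illnesses dominate its variance.

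**The case against.** The strongest reply is that the incidence tests already guard against misreading. In the table's scenarios the log-rank test was significant while the related-AE Fisher test was not in only 0.2%, 0% and 0% of runs. A shorter pooled duration would almost always sit beside a significant excess of reactions. This stands, and it limits the point to a minor one. It does not make the duration p-value interpretable: the report would pair more AEs with significantly shorter AEs, and the second finding would be a by-product of the first.

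Second, the size depends wholly on assumptions, and Protocol 2.4 cites studies in which the full dose raised neither the incidence nor the severity of reactions. That also stands. A reader might infer that the planned test will show significantly shorter AEs for the more reactogenic vaccine. The documents support only that it can, because they give no rate or duration to place this trial in the range.

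Third, the table shells are a separate attachment (SAP 2.1) and may report duration within related and unrelated AEs, where the effect disappears. This is possible, but the SAP text does not say so.

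Fourth, comparing the durations of observed AEs is a legitimate descriptive question, and the SAP attaches no decision to it. This is fair, and it is a reason to present the result as description.

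**Conclusion.** The point holds as a minor one. The pooled log-rank test on AE duration can favour the more reactogenic group through a shift in the mix of events alone. Under the stated assumptions the chance is about 20%, 50% and 80-85% for reaction rates of 15%, 20% and 25% against 10%. It is lower when the two kinds of event differ less in length, and absent when they last equally long.

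A reader might go further and infer that the plan would hide a safety signal or give false reassurance about dose. The documents do not support that: incidence is tested separately in the same section, for related AEs among others, and the listed safety endpoints are incidences. The primary immunogenicity conclusion is untouched. That the test uses only AEs that occurred follows from the definition of duration; the SAP does not state it.

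**What to change.** In SAP 6.9.1:
1. Keep the Kaplan-Meier median durations as descriptive statistics, shown separately for related and unrelated AEs and by solicited term.
2. Drop the pooled between-group log-rank p-value. If a test is kept, run it within related and unrelated AEs, or stratify it by relatedness.
3. State whether the unit is the event or the child.

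Optionally, add AE days per vaccinated child (0 if none) in SS1 and SS2, with a bootstrap 95% CI, as a supplementary summary of burden. Its low power should be noted, about 20% at 10% vs 20% reactions in the scenario above. It should not replace the incidence tests, since a non-significant result could itself be read as reassurance.

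The cost is a few lines of SAP wording and matching table shells. The optional summary needs one variable derived from AE start and end dates that the SAP already uses.

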4.1 Overall Design

This study is a multi-center, randomized, double-blind, controlled trial design. The control vaccines will be Anflu®, trivalent influenza virus split vaccines already marketed by Sinovac (including type B Victoria or type B Yamagata). This trial is a multi-center, randomized, double-blinded, and positive-controlled design. The control vaccine is Anflu®, two 0.25mL-dose trivalent influenza virus split vaccines (TIVs, containing a B Victoria lineage or B Yamagata lineage) marketed by Sinovac. This trial will be conducted on children aged 6 to 35 months with the informed consent of their guardians. A total of 3,300 participants are planned to be recruited and randomly assigned to 4 groups in a ratio of 2:2:1:1, namely the 0.25mL-dose QIV group, 0.5ml-dose QIV group, TIV-BV group, and TIV-BY group. All participants receive 2 doses of the test vaccine or control vaccine according to the 0, 28-day immunization schedule. Among them, subjects aged 6 to 11 months (before their first birthday) will receive intramuscular injections in the anterolateral thigh, and those aged 12 to 35 months will receive intramuscular injections in the deltoid muscle of the upper arm.

Table 4.1.1 Phase III Study Design

Group	Vaccine	Sample Size	Immunization schedule (days)	Antibody test blood collection point (day)
Test Group 1	Influenza Vaccine (Split Virion), Inactivated, Quadrivalent (0.25mL)	1100	0, 28	0, 56
Test Group 2	Influenza Vaccine (Split Virion), Inactivated, Quadrivalent (0.5mL)	1100	0, 28	0, 56
Control Group 1	Influenza Vaccine (Split Virion), Inactivated, Anflu (0.25mL, including BV)	550	0, 28	0, 56
Control Group 2	Influenza Vaccine (Split Virion), Inactivated, Anflu (0.25mL, including BY)	550	0, 28	0, 56
Total	\	3300	\	\

Safety evaluation: All participants are observed for immediate reactions for 30 minutes after each dose, solicited systemic and local adverse events within 0-7 days, and unsolicited adverse events within 0-28 days after each dose. Additionally, monitoring of serious adverse events (SAEs) and adverse events of special interest (AESIs) is conducted from the first dose administration to 6 months after the second vaccination to evaluate the safety.

Immunogenicity evaluation: About 2 to 3mL of venous blood is collected from each subject before vaccination and 28 days after full-course vaccination, respectively, and then the serum is isolated and

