6.1.5 Table and Listing

➤ **Table**

Results will be generally summarized by groups (including test group 1, test group 2, control group 1, and control group 2). Groups are generally presented in the form of columns, and the specific group display will be adjusted according to the actual situation.

➤ **Listing**

Unless otherwise specified, all listings will include group, site, subject number, and the original data will be displayed first. The listing will be generally sorted in sequence by group, site, subject number, visit, or other relevant times (such as the start date of AE).

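### SAP 6.9 plans no QIV-minus-TIV difference or interval for the protocol's safety endpoints; its only rate differences use one 550-child TIV arm at a time, and the printed list omits 0.5 mL QIV against TIV-BY

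*SAP*

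**What the plan says.** Protocol 7.2 names four safety endpoints: adverse reactions on days 0-28 and on days 0-7 after each dose, and SAEs and AESIs from the first dose to six months after the second.

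For these, SAP 6.9.1 to 6.9.3 plan event counts, subject counts and incidences by group and in total, and Fisher's "exact test will be used to statistically test the differences between groups". The general rule in SAP 6.1.1 adds a Clopper-Pearson 95% interval to percentages. SAP 6.1.5 sets the default columns: "Results will be generally summarized by groups (including test group 1, test group 2, control group 1, and control group 2".

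Rate differences between groups appear once, near the end of SAP 6.9.1: "Present the forest plots to compare the differences in the incidence rates of AEs between the two groups". Four contrasts follow: test 1 minus control 1, test 1 minus control 2, test 2 minus control 1, and test 2 minus control 1 again. The terms to plot are chosen "according to the top ten preferred terms for incidence rates in the vaccine group".

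For immunogenicity the plan treats the controls differently. For H1N1 and H3N2, SAP 4.3 says "two control groups are pooled. The sample size ratio of the test group and the pooled control group is 1:1", and SAP 6.7 and 6.8 analyse them that way.

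**The concern.** Safety of both QIV doses is a stated objective and the trial has a concurrent active control. A reader of the results will want to know how far each QIV dose differs from TIV on each named safety endpoint, and how precisely. The plan supplies a p-value for that question but no estimate.

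Where differences are planned, each uses half of the TIV children. Protocol 5.3 and Table 2 describe both controls as 0.25 mL with 7.5 μg per strain, from the same manufacturer, differing in the B lineage. The allocation makes their pool equal in size to each QIV arm, so a matched comparator exists and safety does not use it.

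Two smaller defects sit in the same sentence. The repeated contrast leaves 0.5 mL QIV without a planned comparison against TIV-BY. The vaccine group that ranks the terms is undefined, since all four arms receive a vaccine. If it means a QIV arm, the ranking favours terms that are high in that arm by chance and can leave out of the plot terms that are more frequent under TIV.

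**Working it through.** **Inputs.** SAP 4.3: "the sample size of each test group is 1,100, and the sample size of each control group is 550". SAP 4.1: "randomly assigned to 4 groups in a ratio of 2:2:1:1". The Safety Set takes every randomised child with at least one dose, so the planned arm sizes are used without a dropout deduction. The documents give no adverse event rates, so every rate below is an assumption.

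**The plan's own figures first.** The documents state no safety precision. The nearest figures are the SCR sizes: rate 65%, margin 10 points, one-sided 0.025, power 96% per strain.
- Unpooled normal formula, 1:1: (1.960 + 1.751)² × 2 × 0.65 × 0.35 / 0.10² gives 627 per group, against 625 stated. At 2:1 it gives 470 controls, against 457.
- The score (Farrington-Manning) version gives 624.2 and 456.6, which round up to the stated 625 and 457 (test group 914).
- Dropout: 914 / 0.83 gives 1,102 and 457 / 0.83 gives 551, against 1,100 and 550 planned.

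The arm sizes and the 1:1 pooled comparison are therefore understood correctly.

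**Loss from using one TIV arm, equal rates.** The ratio of standard errors is √[(1/1100 + 1/550) / (1/1100 + 1/1100)] = √1.5 = 1.2247, or 22.5% wider at any common rate.

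Half-width = 1.96 × √[p(1 − p)(1/1100 + 1/n)], with n = 550 or 1,100, in percentage points:

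| Assumed rate | One TIV (550) | Pooled TIV (1,100) |
|---|---|---|
| 1% | 1.02 | 0.83 |
| 10% | 3.07 | 2.51 |
| 20% | 4.09 | 3.34 |
| 30% | 4.69 | 3.83 |

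Miettinen-Nurminen intervals agree. The width ratio is 1.246 at 2%, 1.227 at 10%, 1.225 at 20% and 1.224 at 30%.

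**Unequal rates.** With v = p(1 − p) in each group, the ratio is √[(v_QIV + 2v_TIV) / (v_QIV + v_TIV)].
- QIV 2%, TIV 1%: √[(0.0196 + 0.0198) / 0.0295] = 1.16.
- QIV 1%, TIV 2%: √[(0.0099 + 0.0392) / 0.0295] = 1.29.

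The other pairs tried (10% with 15%, and 20% with 30%, each in both directions) fell between these.

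**The printed contrasts.** Two QIV arms and two TIV arms give four pairs. SAP 6.9.1 lists three distinct pairs and repeats one. The missing pair is 0.5 mL QIV minus TIV-BY.

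**The case against.** The strongest reply is that nothing here breaks a stated rule. The safety objective is secondary and non-comparative. Protocol 7.2 defines the safety endpoints as incidences, no safety margin or hypothesis exists, and the sample size rests on immunogenicity alone. Pooling for H1N1 and H3N2 is justified by antigens that both TIVs contain, and the plan keeps the B-strain comparisons separate. Reactogenicity belongs to the whole product, so the case for pooling does not carry over automatically. All of this stands. It is why the pooled contrast should sit beside the separate ones, and why the point is an improvement and not an error in the main analysis.

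Four stronger readings are tempting, and the documents do not support them.
- A reader might infer that the safety endpoints get no estimate at all. They get per-group incidences with intervals; what is missing is a between-group estimate.
- A reader might infer that the SAP's planned safety intervals are 22% too wide. The SAP defines no interval for an adverse event difference, so the figure describes what a forest plot would imply.
- A reader might infer that every safety comparison throws away half the controls. The SAP does not say whether Fisher's test is pairwise or over all four groups. A four-group test uses all 3,300 children.
- A reader might infer that terms more frequent under TIV vanish. SAP 6.9.1 also tabulates all adverse events and those at or above 1% and 10%, so the ranking rule affects one display.

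A pooled display may also exist elsewhere. Protocol 9.11 was not translated, the table shells are a separate attachment, and SAP 6.1.5 lets the group display be adjusted. That limits the claim to the SAP text, which should still specify the analysis.

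**Conclusion.** The point holds in a limited form. The SAP text plans no QIV-minus-TIV difference or interval for any Protocol 7.2 safety endpoint. Its only rate differences are for ten preferred terms against single TIV arms, with one contrast printed twice and one absent. It never pools the TIVs for safety.

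The cost is precision. An interval against one TIV arm is about 22% wider than against the pool at equal rates, and about 16% to 29% wider over the unequal rates tried. This rests on full planned arm sizes and assumed event rates, and the pooled figure further assumes that the two TIVs have similar reactogenicity. The trial's success criteria are unaffected.

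**What to change.** In SAP 6.9:
- Correct the duplicated contrast so that test group 2 minus control group 2 is listed.
- For each Protocol 7.2 safety endpoint, add 0.5 mL QIV minus pooled TIV and 0.25 mL QIV minus pooled TIV with Miettinen-Nurminen 95% intervals, the method SAP 6.8 already uses for SCR differences. Name the same method for the forest plots.
- Keep the separate TIV columns and single-TIV contrasts beside the pooled ones.
- Choose the ten forest-plot terms by incidence over all four arms, in place of the undefined vaccine group.

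The cost is SAP wording and a few table rows, with no change to trial conduct or data collection. The one downside is the assumption that the two TIVs have similar reactogenicity, which the retained separate columns let readers check.
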